#### Adherence

A high rate of adherence to treatment is required and Investigators are responsible for ensuring that participants understand this. Prior to consent, Investigators and any other trial staff involved in the consent process should ensure that participants fully understand the trial treatment and the importance of adherence, and this should be re-iterated at face-to-face (or telephone) follow-up visits at the specified time points and adherence should be positively encouraged. Patient-reported adherence should be recorded on follow-up CRFs.

Compliance with trial drug will be assessed by pill counting (returns of unused medication). Returns of residual pills will be recorded in accountability logs retained in pharmacy and the electronic Case Report Form (eCRF).

- If treatment ceased for 6 or less days no action taken.
- If ≥7 days record on the CRF.
- If ≥14 days consider restarting with once daily dosing and escalating to twice daily dosing.
- If treatment is paused and >20% of doses are missed for any reason, it is at the discretion of site investigators as to whether it is appropriate to restart trial treatment.
- All treatment pauses must be recorded in the CRF.

IRAS: 1005142 Page **65** of **109** 

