#### 2.5 Assessment and management of risk

This trial is categorised as:

• Type B = somewhat higher than the risk of standard medical care

Use of low dose aspirin (75mg) will minimise the risk of adverse events; this is the lowest clinically used dose of aspirin in adults and is well tolerated.

To minimise the chances of GI toxicity, patients randomised to metformin will start at a dose of 500mg once daily and this will be increased after four weeks to the full dose of 500mg twice daily. Patients will be advised to take their tablets with or after food to help with treatment tolerance. If GI toxicities do occur this will be managed by dose reduction of metformin or a switch to a modified release (MR) preparation according to local policy. Following a drug safety update from the MHRA regarding monitoring patients at risk of reduced vitamin B12 levels, annual testing will be required by sites for participants randomised to the aspirin plus metformin arm only.

If participants experience GI symptoms in the resveratrol sub-trial trial, they will be advised to take their full dose with or after food; if symptoms do not improve, they can divide their dose such that two capsules are taken each morning and two in the evening. It will not be possible to manage these patients by reducing the dose without unblinding the trial because participants in the low 5mg resveratrol dose group take one 5mg capsule and three placebo capsules each day.

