# 8.6 Dosing schedules

The main trial is open-label; the participants, research team and pharmacy team will be aware of the treatment assignment.

Eligible participants will be randomised at visit 1 to receive Aspirin 75 mg Gastro-Resistant tablets once daily OR Aspirin 75 mg Gastro-Resistant tablets once daily AND Metformin hydrochloride 500 mg film-coated tablets twice daily.

All participants will be given a dose instruction card describing when to take the medicine, how to take the medicine and the dose.

There will be no weight-based dosing for this trial. All trial drugs are self-administered.

One 75 mg tablet of aspirin will be taken daily and swallowed whole with plenty of liquid (e.g. a glass of water) preferably after a meal. The participant will take their aspirin dose at a similar time each day ensuring sufficient intervals between dosing. A low dose of aspirin has been selected for the trial reducing the likelihood of toxicity. The maximum daily aspirin dose for this trial is 75 mg, and no dose interruptions are anticipated in the absence of specific adverse events. See section 8.7.

IRAS: 1005142 Page **60** of **109** 

Metformin 500mg will be started once daily for 4 weeks. One tablet will be taken orally with breakfast. For the purposes of this clinical trial we are allowing a 4 week run-in to maximise gastrointestinal tolerability. The research team will contact the participant by telephone, 4 weeks after randomisation to check for any adverse effects. If the participant is tolerating the 500 mg dose of metformin, they will be advised to increase their dose twice daily with one tablet to be taken with breakfast and one tablet to be taken with their evening meal. If tolerated, the maximum daily dose of metformin will be 1 g for the remainder of the trial. See section 8.7 for guidance on definition of tolerability and dose modification in the presence of specific adverse events.

The trial pharmacy team will dispense sufficient IMP to last for the full 6 month interval between out-patient visits, see schedule below.

Dispensing schedule			
Visit #	Time point		
Visit 1	Baseline (week 0)		
Visit 4	Week 25		
Visit 5	Week 52		
Visit 6	Week 78		
Visit 7	Week 104		
Visit 8	Week 130		
Visit 9	No dispensing. Stop dosing on day of exit surveillance colonoscopy - anticipated at week 154		

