# 8.7 Dosage modifications

# Aspirin

Aspirin dose cannot be modified, only stopped.

Patients will be made aware that aspirin should be used with caution before surgery, including tooth extraction. Temporary discontinuation of treatment may be necessary.

Participants that experience any aspirin-related severe toxicity (defined as ≥grade 3 Common Terminology Criteria for Adverse Events (CTCAE v5)) or significant gastrointestinal bleeding (grade 3 and 4), active gastrointestinal ulceration, new cases or worsening tinnitus (grade 2 or above), intracranial bleeding or hypersensitivity to aspirin should permanently discontinue aspirin immediately.

IRAS: 1005142 Page **61** of **109** 

COLO-PREVENT Protocol 11/12/2024: Version 4.0

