#### **Metformin**

#### Run-in

Undesirable effects of metformin are most frequent during initiation of therapy and usually resolve spontaneously. To prevent them, it is recommended that metformin is taken during or after meals. Metformin does not cause hypo-glycaemia in non-diabetic patients and participants will be reassured about this prior to dosing. Participants will have a run-in period of 4 weeks at the once daily 500 mg metformin dose to allow time for gastrointestinal tolerance. If more than 80% of the prescribed dose is taken during this time, the research team will instruct the participant to increase their dose to twice daily 500 mg metformin tablets.

If the patient does not tolerate the 500 mg metformin then it is possible for the patient to have another 4 week run-in period using a MR formulation 500 mg dose. If this is deemed tolerable then patients will increase their dose to twice daily 500 mg MR release metformin tablets. If the participant is unable to tolerate the lowest dose of metformin then they can continue on the trial with aspirin alone.

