#### Main trial

It is advised that metformin treatment will be paused for approximately 72 hours around the time of contrast-enhanced CT scans.

Metformin must be discontinued at the time of surgery under general, spinal or epidural anesthesia. Therapy may be restarted no earlier than 48 hours following surgery or resumption of oral nutrition and provided that renal function has been re-evaluated and found to be stable.

Metformin must be permanently discontinued in patients where the GFR < 30mls/min. Patients who develop acute and unstable heart failure, while on the study should discontinue metformin.

For patients who wish to stop metformin due to adverse events then they should be offered a trial of twice daily 500 mg MR formulation to improve tolerability. If adverse events persist then the metformin dose can be reduced to 500 mg once per day. No further dose modifications are permitted and therefore if adverse events continue the metformin should be permanently discontinued.

If a participant misses >20% of doses for aspirin in combination with metformin or aspirin alone, then it is at the discretion of site investigators as to whether it is appropriate to restart trial treatment.

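### Protocol sections 2.5, 8.7 and 8.11 do not agree on metformin dose changes, and 8.11 does not say whether its restart rule covers participants already reduced for adverse events

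*Protocol*

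**What the plan says.** Four places in the protocol bear on the metformin dose in the main trial.

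- **Section 2.5 (risk).** If gastrointestinal toxicity occurs, "this will be managed by dose reduction of metformin or a switch to a modified release (MR) preparation according to local policy". Two measures are named, with no order between them.
- **Section 8.6 (dosing schedules).** This refers the reader to 8.7 for the meaning of tolerability and for dose modification when specific adverse events occur.
- **Section 8.7 (dosage modifications, metformin).** In the run-in, a participant who does not tolerate 500 mg once daily may have a second four weeks on MR 500 mg: "If this is deemed tolerable then patients will increase their dose to twice daily 500 mg MR release metformin tablets". After the run-in, for patients who want to stop metformin because of adverse events, "they should be offered a trial of twice daily 500 mg MR formulation to improve tolerability". Then: "If adverse events persist then the metformin dose can be reduced to 500 mg once per day. No further dose modifications are permitted". If adverse events continue, metformin is stopped for good.
- **Section 8.11 (adherence).** In a list of actions by length of treatment interruption: "If ≥14 days consider restarting with once daily dosing and escalating to twice daily dosing". The bullet names no product and makes no exception.

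On aspirin, 8.7 says "Aspirin dose cannot be modified, only stopped" and 8.6 says "The maximum daily aspirin dose for this trial is 75 mg".

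**The concern.** A site dealing with metformin toxicity can find different instructions depending on which section it opens. Under 2.5 it may reduce the dose without trying MR first. Under 8.7 MR comes first.

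A site restarting a participant after two weeks off treatment finds in 8.11 a path that ends at twice daily. It finds nothing there about a participant whose once-daily dose was set because twice daily was not tolerated.

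Two things are at stake. The first is participant safety and equal handling across roughly 60 sites. The second is how compliance is classified. Section 14.5 has deviations recorded, and section 11.5 defines the per-protocol population by the absence of a protocol violation. A site that follows 2.5 or 8.11 may be departing from 8.7, so who counts as a violator could depend on which section is taken as the rule.

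**Working it through.** The document states no figure on this point to reproduce, so the check is a comparison of the text.

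**Step 1: order of measures, 2.5 against 8.7.**

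| | 2.5 | 8.7 (after run-in) |
|---|---|---|
| Trigger | Gastrointestinal toxicity occurs | Patient wishes to stop because of adverse events |
| First measure | Reduction or MR | MR 500 mg twice daily |
| Second measure | None stated | 500 mg once daily, if adverse events persist |
| After that | None stated | No further modification; permanent stop if events continue |
| Who sets the order | Local policy | The protocol |

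The measures are the same, but the order, the trigger and the source of the decision differ. If the reference to local policy attaches only to the MR switch, 2.5 still offers alternatives where 8.7 sets a sequence.

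**Step 2: after a reduction, 8.7 against 8.11.** The rules have different triggers: adverse events in 8.7, length of interruption in 8.11. They meet only in a participant who (a) was reduced to once daily under 8.7 and (b) later has 14 days or more off treatment. For that participant 8.7 permits no further modification, while 8.11 lets the site consider a return to twice daily. Neither section refers to the other on this point or says which prevails. The case is foreseeable: 8.7 itself requires metformin to stop for surgery under general, spinal or epidural anaesthesia. It gives the earliest restart but no restart dose.

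**Step 3: which drug 8.11 means.** Metformin is the only main-trial drug with a step from once to twice daily (8.6 and the run-in text of 8.7). Aspirin is one 75 mg tablet a day and its dose cannot be changed. The parallel list for the sub-trial in 9.11 repeats the other four bullets and omits this one, as expected of a rule meant for metformin. The drug can be identified, but only by inference.

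**Step 4: number affected.** Section 11.1 plans 862 participants, 431 per arm, so the restart rule can reach at most the 431 allocated metformin. Those meeting both (a) and (b) are a subset. The protocol gives neither a dose-reduction rate nor a rate of pauses of 14 days or more, so the subset cannot be sized.

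**The case against.** The strongest reply is that this is a drafting gap and not a contradiction. Section 2.5 is a risk overview, 8.6 points to 8.7 for dose modification, and 8.7 can be taken to govern. Section 8.11 only asks sites to *consider* the step. Once more than 20% of doses are missed, restart is at the investigator's discretion. For a participant already reduced, the words of 8.7 would on their face bar a return to twice daily.

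Much of this stands. Nothing instructs a site to re-escalate such a participant; the possibility comes from a missing exception. It does not remove the point, because 2.5 and 8.7 still differ on order, and 8.11 is an operative section that neither yields to 8.7 nor mentions it.

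Three stronger readings are tempting, and the document does not support them.

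- **Aspirin could be escalated to twice daily, so all 862 participants are exposed.** This requires ignoring the aspirin limits in 8.6 and 8.7. The missing drug name is a wording gap.
- **About 86 to 129 participants are affected** (431 × 0.20 = 86; 431 × 0.30 = 129). The 20–30% in section 1.3.3 is the share of metformin users in general with gastrointestinal symptoms. It is not a rate of dose reduction in this trial. The up to 5% who stop because of severity, in the same sentence, would give about 22 (431 × 0.05 = 21.6), also only a rough proxy.
- **The trial's results are compromised.** The primary approach in 11.3 is intention-to-treat, and dose reduction is not a listed outcome in section 3.5. No effect on a result can be shown from the text.

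**Conclusion.** The concern holds as a failure of alignment between operative dosing passages. Sections 2.5 and 8.7 differ on the order of measures and on who sets it. Section 8.11 does not name the drug it covers, and it leaves open whether a participant reduced to once daily for adverse events may be considered for twice-daily dosing after a pause of 14 days or more, although 8.7 permits no further modification.

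The size is unknown and bounded: for the restart rule, some part of the 431 in the combination arm. The conclusion rests on two readings: that 8.11 means metformin, and that the bar in 8.7 covers upward as well as downward changes. If the bar was meant only to rule out further reductions, the clash with 8.11 weakens, but the protocol should then say so.

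The point should be corrected, because it concerns dosing and consistency between sites and the correction is easy. It is not a reason to doubt the design, the sample size or the primary analysis.

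**What to change.** Reconcile the three passages so that one section carries the rule and the others refer to it.

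1. In 2.5, replace the reference to local policy with a reference to 8.7. If local choice is intended, align 8.7 with it instead.
2. In the 8.11 bullet on interruptions of 14 days or more, name metformin.
3. In the same bullet, state how it applies to a participant already reduced to once daily under 8.7, and refer to 8.7.

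Which sequence and which restart rule are right is for the sponsor's clinicians; the request is only that the protocol state one. The cost is protocol wording. The one downside is that sites may lose the discretion 2.5 now gives them.

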# 9. SUB-TRIAL THERAPIES

# 9.1 Name and description of investigational medicinal products

The Signal-Seeking **Sub-Trial is anticipated to start in early 2023**. Once all required data is obtained from the manufacturer, a major Substantial Amendment (SA) will be submitted. The resveratrol sub-trial will not commence until regulatory approval is in place for the SA.

The Investigational Medicinal Product (IMP) for the sub-trial is resveratrol.

Veri-teTM *trans*-Resveratrol (CAS number: 501-36-0) is the Active Pharmaceutical Ingredient (API) being used to manufacture capsule strengths of 5 mg and 250 mg

# **Chemical product name:**

#### Molecular formula:

(E)-5-(4-hydroxystyryl)benzene-1,3-diol;

5-[(1E)-2-(4-Hydroxyphenyl)ethenyl]-1,3-benzenediol

trans (E) resveratrol

The Veri-teTM trans-Resveratrol is produced yeast (Saccharomyces cerevisiae) fermentation (using renewable feedstock/source as the carbon source, followed by separation and purification). Resveratrol API is manufactured in Italy, in a facility operating under cGMP and HACCP standards. Veri-teTM is a trademark of Evolva SA (headquarter address: [name]).

The sub-trial is double-blinded, and eligible participants will be randomised to receive 5 mg resveratrol or 1 g resveratrol (4X 250 mg) or placebo to be taken once daily for 1 year.

Drug Name	Dosage	Description
Resveratrol	5 mg (OD)	Hydroxypropyl methylcellulose (HPMC) capsules containing 5 mg trans -Resveratrol; excipient blend TBC
Resveratrol	250 mg (OD)	Hydroxypropyl methylcellulose (HPMC) capsules containing 250 mg trans -Resveratrol; excipient blend TBC

The resveratrol capsules and matching placebo are being manufactured by Catalent Pharma. Final labelling and release of blinded IMP/placebo packs will be carried out by Catalent Pharma. All sites involved in the manufacturing process have appropriate licenses in place.

Resveratrol 5 mg, resveratrol 250 mg and placebo will be filled into identical, same sized capsules and weight-matched. Both of the active doses of resveratrol and the placebo will be packaged in an identical manner. A unique pack ID will be used to identify each pack and its contents.

IRAS: 1005142 EudraCT: 2022-000531-23

# 9.2 Regulatory status of the drug

There are no marketing authorisations for resveratrol in the UK or indeed worldwide.

Resveratrol is a naturally occurring phytoalexin, an antifungal and antibacterial chemical produced by plants in response to stress, and is found in a variety of food and drinks including red wine, grapes, and peanuts. Resveratrol is widely sold as a single supplement or constituent of a supplement in health food shops in the UK, and resveratrol-containing nutraceutical products are available in capsule, tablet, film, and chewing gum formats.

#### 9.3 Product Characteristics

The Investigator Brochure (IB) for resveratrol will be used to obtain information on how to use the medicine and to assess expectedness of events (section 8.0 of the IB is known as the reference safety information). The IB will be provided in the Investigator and Pharmacy Site Files.

# 9.4 Drug storage and supply

Catalent Pharma will store bulk IMP supply and distribute blinded trial drug to participating centres. The resveratrol/placebo will be provided to sites free of charge.

Participating sites will be allocated an initial supply of resveratrol/placebo at site activation. Stock levels will be monitored by the clinical trials pharmacy team and the trial management team at LCTU. When trial drug supplies reach a pre-determined level resupply will be arranged.

Storage conditions will be in compliance with the Investigators Brochure. At site the resveratrol/placebo will be stored between 15-25°C. Storage of trial drug at site will be in a secure location, in a temperature controlled environment, with a temperature log maintained for each working day.

Any temperature excursions must be reported to the Leicester CTU and Sponsor as soon as they are identified.

The local site investigator will delegate responsibility to the Clinical Trials Pharmacist to ensure drug accountability, including reconciliation of trial drug and maintenance of trial drug records, throughout the course of the trial in accordance with UK regulatory requirements. Trial drug may be dispensed only by specifically authorised personnel. Responsibility for certain tasks related to the management of the trial drug can be delegated to the site pharmacy clinical trials staff and other members of the site team.

Trial drug allocated to a participant must not be used for any other purpose than the present trial. Prescriptions should be made available for review as source data.

Dispensing will be recorded on the appropriate trial specific accountability forms. Trial drug that has been dispensed to a participant must not be re-dispensed or re-issued to a different participant.

IRAS: 1005142 Page **67** of **109** 

Unused drug, partially used drug and empty packaging will be returned to research staff at the 6 monthly visits (see table 1), the surveillance colonoscopy or post-colonoscopy visit. Unused drug, partially used drug and empty packaging will be taken to the local pharmacy to be recorded and final accountability performed before local destruction is approved by the Sponsor.

# 9.5 Preparation and labelling of Investigational Medicinal Product

Final labelling and QP release of blinded trial drug packs will be carried out by Catalent Pharma, in line with Annex 13 of the EU Guidelines for Good Manufacturing Practice.

Catalent Pharma will arrange for delivery of the labelled resveratrol/placebo to the recruiting site at regular intervals according to trial requirements. Allocation of trial medication (resveratrol 5mg or resveratrol 1 g or placebo) will be managed by Sealed Envelope (web based randomisation system). The participant, research team and pharmacy team will all be blinded to the treatment allocation.

# 9.6 Dosing schedules

The sub-trial is double-blinded; the participants, research team and pharmacy team will not be aware of the treatment assignment.

Eligible participants will be randomised at visit 1 to receive one of the following BLINDED allocations:

- 5 mg resveratrol intervention arm
- 1 g resveratrol intervention arm
- Placebo arm

The capsules will be packaged into bottles. Each patient kit will contain 4 bottles such that patients take one capsule from each bottle daily. The 3 types of blinded kit will comprise of the following:

- **5mg resveratrol intervention arm:** 1 bottle of 5mg resveratrol capsules + 3 bottles of placebo
- 1g resveratrol intervention arm: 4 bottles of 250mg resveratrol capsules
- Placebo arm: 4 bottles of placebo capsules

There will be no weight based dosing for this trial. All trial drugs are self-administered.

The web based randomisation system will generate a unique kit ID which will be added to a trial specific prescription, along with the participant's trial number and details.

All participants will be given a dose instruction card describing when and how to take the medicine.

IRAS: 1005142 Page **68** of **109** 

The research team will be conducting telephone consultations at visits 2 (week 4) and 3 (week 12) and will ask the participant about any symptoms or new medical problems since the last contact. Participants will be reminded to take their trial drug as directed.

Dispensing will be recorded on the appropriate trial specific accountability forms. Trial drug that has been dispensed and prepared for administration to a participant must not be redispensed or re-issued to a different participant.

